4.3 Rationale for choice of control drugs (comparator/placebo) or combination drugs

Not applicable.

4.4 Purpose and timing of interim analyses/design adaptations

There will be two planned interim assessments performed:

1. after all patients in Cohort 1 have completed Day 43 (core study period), when key efficacy and safety parameters and PK exposure data will be assessed in order to determine whether to proceed to Cohort 2 and if so, to select the starting dose for that Cohort.
2. after all patients in Cohort 2 have completed Day 43 (core study period), when efficacy and safety parameters and PK exposure data from both cohorts will be assessed

PK exposure checks (including safety and efficacy data review as available) will also be performed as described in [Section 3](#), [Section 4.2](#) and [Section 12.7](#).

The PBPK model will be updated and qualified periodically with the available PK data from Cohort 1 and/or Cohort 2 and additional interim assessments including PBPK simulations may be used to support a recommendation of an appropriate dose for this population.

4.5 Rationale for public health emergency mitigation procedures

During a public health emergency as declared by local or regional authorities e.g., pandemic, epidemic, or natural disaster, mitigation procedures to ensure participant safety and trial integrity may be implemented. Notification of the public health emergency as declared by local or regional authorities should be discussed among investigators and Novartis. All procedures adapted to the situation must be submitted, if required as per local regulations, through a protocol amendment for approval by local or regional Health Authorities and Ethics Committees prior to implementation of mitigation procedures.

4.6 Risks and benefits

The safety and efficacy of Coartem®/Riamet® has been characterized in adults and pediatric patients ≥ 5 kg BW.

The safety profile of the current Coartem®/Riamet® 6-dose regimen has been well-characterized in approximately 6000 patients in Novartis-sponsored clinical trials (almost 500 of them having received the dispersible tablet). There have been two pooled safety analyses of randomized clinical trials data performed, one including 712 adolescent/adult patients (i.e., patients > 12 years of age and ≥ 35 kg BW) and another including 1262 infants and children (i.e., patients < 12 years of age and ≥ 5 kg to < 35 kg BW) treated with the standard tablet or dispersible tablet formulation according to the 6-dose regimen. Overall, Coartem®/Riamet® is well tolerated in both pediatric and adult patients. The profile and frequency of adverse events seems comparable between these patient populations. A majority of the adverse events reported in these studies could also have been attributed to malaria: they were rated mild to moderate in intensity and not necessarily related to artemether-lumefantrine. Furthermore, extensive post-marketing experience confirmed that Coartem®/Riamet® (artemether:lumefantrine 20 mg:120 mg) has a well characterized risk-benefit profile. Currently, clinical data available in patients < 5 kg were collected in study B2306 in 20 patients > 28 days of age. In that study, artemether exposure following administration of the 6-dose regimen of Coartem® (one artemether:lumefantrine 20 mg:120 mg dispersible tablet/dose) was around 2-3 fold higher than anticipated safe exposures, whereas exposure to lumefantrine was as expected. Given the potential neurotoxicity of artemether at high exposures, and based on preclinical data, it was decided not to proceed with the second cohort of the same study (infants ≤ 28 days of age).

The safety profile associated with a higher systemic artemether exposure could not be fully supported by preclinical data:

- in dogs, pathological evidence of neurotoxicity was noted with intramuscular doses of artemether administered daily for 8 days.
- monkeys were less susceptible to artemether-induced neurotoxicity ([Li and Hickman 2011](#)).

The risk to subjects in the present trial will be minimized by excluding neonates/infants with critical conditions, through ensuring close clinical monitoring, and in-patient status (during the treatment period). Regular safety laboratory measurements will be used including hematology and blood chemistry tests, in order to ensure a close monitoring beyond the hospitalization period.

Furthermore, pain and fever control methods will be implemented at the investigator's discretion including appropriate use of antipyretics (e.g., during and after a painful procedure such as venipuncture). In terms of PK assessments, a sparse blood sampling strategy ([Djimdé et al 2011](#)) will be used. The total blood volume drawn over 6 weeks in this population will not exceed the limit of 2.4 to 2.7 mL per kg BW, following WHO recommendations ([Howie 2011](#)). In case of severe anemia developing during the study, the total blood volume drawn should be adjusted downwards as necessary at the investigator's discretion.

Finally, a DMC will be established to safeguard patient safety (see [Section 10.2.1](#)). The DMC will meet at regularly scheduled time points to review the PK, efficacy and safety data collected. The responsibilities and specific aspects of the DMC are described in the DMC charter.

Hence, based on the risk-benefit profile and unmet medical need, Novartis has considered justified to explore the use of artemether:lumefantrine (1:12) in acute, uncomplicated *P. falciparum* malaria-infected infants and neonates <5 kg BW through the present study (B2307).

5 Population

The study population will consist of a representative group of neonates and infants of both sexes with a BW <5 kg and a confirmed diagnosis of acute uncomplicated *P. falciparum* malaria or mixed infections by microscopy with asexual *P. falciparum* parasitemia of ≥ 500 and $< 100,000$ parasites/ μL in Cohort 1 and of ≥ 100 and $< 100,000$ parasites/ μL in Cohort 2.

The study population will be enrolled in two sequential cohorts, infants >28 days of age (Cohort 1) and term neonates ≤ 28 days of age (Cohort 2). Cohort 2 is further divided into 3 age subgroups (15-28; 8-14; 1-7 days). In order to obtain for the primary endpoint approximately 16 evaluable neonates/infants exposed to an adequate dose in each cohort, it is planned to have approximately 22 neonates/infants entering the study and exposed to an adequate dose in each cohort. In the event no suitable dose can be determined in the highest age subgroup (15-28 days)

of Cohort 2 or recruitment is not feasible, the cohort will be closed and an additional 22 patients will instead be recruited in Cohort 1 and treated with the dose that was deemed adequate. Additionally, PBPK modeling may be explored with existing data from Cohort 1 to support the dose recommendation in the study population.

Patients will be recruited at approximately 10 sites across 8 countries in Sub-Saharan Africa. Reflecting the local legal and cultural context, effective community engagement will be sought and ensured by the clinical site team.

5.1 Inclusion criteria

Subjects eligible for inclusion in this study must meet **all** of the following criteria:

1. Male or female neonates / infants
2. Body weight <5 kg but ≥ 2 kg
3. In Cohort 1, infants aged >28 days; in Cohort 2, neonates aged 1 to ≤ 28 days (3 subgroups: 15-28 days; 8-14 days; 1-7 days)
4. Microscopically confirmed diagnosis of *P. falciparum* malaria (or mixed infections)
 - in Cohort 1: of ≥ 500 and $<100,000$ parasites/ μ L asexual *P. falciparum* parasitemia
 - in Cohort 2: of ≥ 100 and $<100,000$ parasites/ μ L asexual *P. falciparum* parasitemia
 - either congenital or neonatal
 - either symptomatic or asymptomatic
5. Parental/legal guardian informed consent obtained and signed prior to any study related procedure. If the parent/legal guardian is unable to read or write, then a witnessed consent according to local ethical standards is permitted (formally documented and witnessed, via an independent trusted witness)
6. The parent/legal guardian is able to understand and comply with protocol requirements, instructions and protocol-stated restrictions for their child and is likely to complete the study as planned

5.2 Exclusion criteria

Subjects meeting any of the following criteria are not eligible for inclusion in this study:

1. Head circumference $< - 2$ SD z-score in cm following WHO age and sex-specific reference curves (suspicion of microcephaly) (See [Section 16.1 Appendix 1](#))
2. Severe malnutrition (body mass index (BMI) less than 70% of median normalized WHO reference weight)
3. Presence of severe malaria (according to WHO 2015 definition - See [Section 16.4 Appendix 4](#))
4. Hemoglobin < 7 g/dL
5. HIV status:
 - in Cohort 1 : patient's or patient's mother's current treatment with ARV
 - in Cohort 2 : Mother's known HIV positive status at patient's birth or mother's current treatment with ARV
6. Presence of the following signs of a critical condition: apnea-bradycardia, sustained bradycardia, tachycardia, desaturation, hypotension, hypothermia; or other severely

deteriorated general condition (based on IMCI criteria in sick infants, WHO 2005 - See [Section 16.5 Appendix 5](#))

7. Presence of any clinically significant neurological condition:
 - any episode of convulsion during the present illness (in keeping with the IMCI list of general danger signs)
 - known neurological disorders (e.g. chronic seizure disorders, cerebral palsy)
8. Presence of clinically significant abnormality of the hepatic and renal systems
9. History of malabsorption or previous gastrointestinal surgery, or history of radiation therapy that could affect drug absorption or metabolism, or any other disorder or history of a condition that could interfere with drug absorption, distribution, metabolism, or excretion
10. Patients unable to swallow or whose drinking is impaired
11. Known hypersensitivity of the patient or either patient's parent to artemether, lumefantrine, any of the excipients of Coartem®/Riamet® Dispersible tablet, or to drugs of similar chemical classes
12. Known family history of congenital prolongation of the QT_c interval or sudden death or with any other clinical condition known to be associated with prolongation of the QT_c interval such as history of symptomatic cardiac arrhythmias, with clinically relevant bradycardia or with severe cardiac disease
13. Disturbances of electrolyte balance (e.g. hypokalemia or hypomagnesemia) - See [Section 16.1 Appendix 1](#) as an example for reference
14. Presence of any age-adjusted clinically or hematologically relevant laboratory and blood chemistry abnormalities
15. Patients who received any antimalarial drug, including antibiotics with antimalarial activity, within 14 days of trial start, or any other prohibited drug (see [Table 6-2](#))
16. Patients who received an investigational drug within 5 half-lives of enrollment or participated in an investigational study or within 30 days, whichever is longer.

NOTE: Where information is either not available or insufficient (e.g. from medical history, charts) to assess whether a patient meets a specific exclusion criterion, the study site team shall use its best medical judgement to make an inclusion/exclusion decision for the patient.

6 Treatment

6.1 Study treatment

6.1.1 Investigational and control drugs

Novartis will supply artemether:lumefantrine 2.5 mg:30 mg (COA566 2.5 mg:30 mg) as an investigational product in the form of open label patient specific supplies (see [Table 6-1](#)).

Table 6-1 Investigational and control drug

| | |
|-----------------------|---|
| Treatment Title | COARTEM/RIAMET, COA566 |
| Treatment Description | dispersible tablet, 2.5 mg artemether / 30 mg lumefantrine, 1 to 4 tablets per dose, BID for 3 days, open label |

| | |
|-------------------------|---|
| Type | drug |
| Dose Formulation | dispersible tablet |
| Unit Dose Strength(s) | 2.5 mg artemether / 30 mg lumefantrine |
| Dosage Level(s) | 1 to 4 tablets per dose, BID for 3 days |
| Route of Administration | oral |
| Use | experimental |
| IMP | yes |
| Sourcing | provided centrally by the sponsor |
| Packaging and Labeling | Study treatment will be provided in blisters. Each blister will be labeled as required per country requirement. |

6.1.2 Additional study treatments

No other treatment beyond investigational drug is included in this trial.

6.1.3 Treatment arms/group

Patients will receive artemether:lumefantrine 2.5 mg:30 mg dispersible tablet. Although it is anticipated to have one dose level assessed in the study, four possible dose levels (1 to 4 tablets per dose) may be used (See [Section 6.5.1.2](#)).

In Cohort 1, a regimen of two dispersible tablets (i.e., 5 mg:60 mg artemether:lumefantrine) twice daily for 3 consecutive days will be administered as a starting dose to the first 9 patients. Following a PK check (including safety and efficacy data review as available), the dose level may be adjusted and administered to another 9 patients (up to two re-runs, see [Figure 3-2](#) and [Table 6-3](#)). Once a suitable dose has been determined in 9 patients, about 13 additional patients will be recruited and administered the same dose.

Cohort 2 will be further divided into 3 age subgroups. A PK check will be performed after 3 patients have been treated in the highest age subgroup (15-28 days). In the event the exposure is not considered adequate (see [Section 4.2](#)), the dose may be adjusted and administered to another 3 patients of that age subgroup (up to two re-runs, see [Figure 3-1](#) and [Table 6-3](#)).

For more details, see [Section 3](#).

In case the suitable dose would not be the same across the 2 cohorts, or within Cohorts, treatment groups will be defined based on dose level.

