An Independent Data Monitoring Committee (DMC) will review the PK, efficacy and safety data at these checks, and also at two planned interim data assessments, one between the two cohorts, and another one after all patients in Cohort 2 have completed Day 43 (Figure 3-2).

The interim data assessment based on Cohort 1 data will serve to determine the starting dose level for Cohort 2 (for further details see [Section 10.2.1](#)).

Based on these checks, the dose being considered will be assessed as suitable or not for the subgroup of patients treated.

In Cohort 1:

- if the dose is deemed adequate in the first 9 patients (based on PK, safety and efficacy data review as available), additional patients will be recruited up to approximately 22 treated with the same dose level (expansion phase).
- if the dose is not adequate, the first set of 9 patients will be repeated, up to twice, using a different dose level, until a dose level is determined as suitable.

In Cohort 2:

- if the dose is deemed adequate in the 3 patients from the highest age subgroup (15-28 days), recruitment of 6 additional patients in the 1-28 day subgroup will be attempted.
- if the dose is not adequate, the first set of 3 patients from the highest age subgroup (15-28 days) will be repeated, up to twice, using a different dose level, until a dose level is determined as suitable. Then, recruitment of 6 additional patients in the 1-28 day subgroup will be attempted.

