12.5.3 Pharmacokinetics

The PK set will be used for all PK analyses. Artemether, DHA and lumefantrine plasma concentration and AUC data (as applicable) will be listed by cohort, treatment group, subject, and visit/sampling time point. Descriptive summary statistics will be provided by cohort, treatment group, and visit/sampling time point, including the frequency (n, %) of concentrations below the lower limit of quantification (LLOQ) and reported as zero.

Summary statistics will include mean (arithmetic and geometric), SD, CV (arithmetic and geometric), median, minimum, and maximum. PK concentrations below the LLOQ will be treated as zero in summary statistics and for the calculation of pharmacokinetic parameters by non-compartmental analysis. A geometric mean will be calculated using half LLOQ value for concentrations below LLOQ.

For each PK parameter, the 90% confidence intervals will be calculated on the natural log scale and then anti-log transformed back to the original scale for the following comparisons:

- Artemether vs. historical data (Reference)
- DHA vs. historical data (Reference)
- Lumefantrine vs. historical data (Reference)

Artemether, DHA and lumefantrine PK is considered to be comparable with historical data if the 90% confidence interval contains the Historical values.

For review of the first 9 patients in each cohort (treated with the same dose) and the first 3 patients in each subgroup or optional PK checks in Cohort 2, the following data at all time points will be used to make a decision on a potential dose modification:

- ART C_{max} (higher concentration between the concentrations at 1 hour and 2 hours post first dose) (Primary)
- Day 8 (168 h) lumefantrine concentration
- C_{max} of DHA following the first dose from patients providing 1 h and 2 h data
- C_{max} of artemether and DHA following the last dose from patients providing 1 h and 2 h data
- C_{max} of lumefantrine from patients providing data after the last dose (due to potential accumulation for lumefantrine).

For the first 3 patients in each age subgroup in Cohort 2, the PK check is intended to make sure that the exposure for these patients is within the expected safety interval based on the historical data.

For the first 9 patients in each cohort or optional PK checks, the PK review is intended to check if the C_{max} is within approximately 2-fold of the C_{max} which has been found to be safe and efficacious in previous studies.

[figure not shown]

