2.5.4 Supportive analyses

Sensitivity analyses

Ninety percent (90%) 2-sided confidence intervals for the geometric mean of ART C_{max} will be calculated based on the log normal distribution by cohort and treatment group using the PPS. Patients with missing ART C_{max} will be excluded from the analysis.

Supportive analyses

If there are treatment groups that are used for multiple cohorts, ninety percent (90%) two -sided confidence intervals for the geometric mean of ART C_{max} will be calculated for these treatment groups based on the log normal distribution using the PK set by pooling data from all cohorts.

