5.7 Statistical models

5.7.1 Primary analysis

The primary analysis is detailed in [Section 2.5](#).

The primary endpoint ART C_{max} will be displayed by cohort and treatment group using the geometric mean. The geometric mean will be calculated by deriving the mean of the log-transformed values followed by an exponential transformation, i.e. *Geometric Mean (GM) = e^{mean(log(x))}* with x = ART C_{max} of a participant.

Corresponding 2-sided 90% confidence intervals for the GM will be calculated assuming a log normal distribution of the primary endpoint. The lower and upper limits will be calculated as follows:

$$\exp(\bar{x} \pm t_{(1-\frac{\alpha}{2};n-1)} \times \frac{s}{\sqrt{n}})$$

with \bar{x} = the arithmetic mean of the log-transformed endpoint, $t_{(1-\frac{\alpha}{2};n-1)}$ = the $(1 - \frac{\alpha}{2})$ critical value of the Student's t statistic with $n - 1$ degrees of freedom, s = the standard deviation of the log-transformed endpoint, and n = the number of patients with available endpoint in the corresponding cohort and treatment group.

The logarithm to the natural base is used.

The calculation will be implemented in SAS using PROC MEANS on log data followed by an exponential transformation.

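### Patients whose artemether Cmax helps decide that a dose is kept are re-used unadjusted in the final 90% CI, so if a dose at 2-fold exposure or more survives the check, the reported exposure is too low; no planned analysis shows this.

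*Protocol*

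**What the plan says.** **The check.** Protocol 12.5.3 lists five PK items, with ART Cmax first and marked primary, that "will be used to make a decision on a potential dose modification". For the first 9 patients, "the PK review is intended to check if the C_{max} is within approximately 2-fold of the C_{max} which has been found to be safe"; the comparison is with earlier trials. No statistic (geometric mean, confidence interval or individual values) is attached to the 2-fold margin. Protocol Section 3 makes the decision wider than PK: expansion follows "if the dose is deemed adequate in the first 9 patients (based on PK, safety and efficacy data review as available"). Protocol 12.7 calls the checks informal and sends them to the DMC. Cohort 2 is checked at 3 patients and again at 9.

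**The expansion.** Protocol 6.1.3: "Once a suitable dose has been determined in 9 patients, about 13 additional patients will be recruited and administered the same dose". The check patients therefore count towards the approximately 22.

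**The final interval.** SAP 5.7.1 gives a t interval on log Cmax, with n defined as "the number of patients with available endpoint in the corresponding cohort and treatment group". The PK set (Protocol 12.1, SAP 2.2) requires only evaluable PK data, so the check patients stay in.

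**Sensitivity and supportive analyses.** Protocol 12.4.4 and SAP 2.5.4 plan the same interval in the PPS and an interval pooled across cohorts. Neither removes the check patients.

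**The concern.** A dose that is truly too high is kept only when its first patients happen to show low values. Those low values then enter the final mean and are treated as an unselected sample. With 9 of about 22 patients they are 41% of the data; with 8 of 16 evaluable they are 50%. The mean is pulled down and the upper limit comes out too low.

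The upper limit matters most here. The trial was set up because an earlier study found artemether exposure 2 to 3 times that in larger children (Protocol 4.2). Readers will use the final geometric mean and its upper limit to judge how high exposure may be at the recommended dose.

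**Working it through.** **1. The plan's own figure.** Protocol 12.8.1 states that 16 evaluable patients give 80% probability of a 90% CI half-width of at most 0.337 at SD 0.65. The formula is P = P(χ²[n−1] ≤ (n−1)(0.337√n / (t × 0.65))²), with t = t(0.95, n−1). It gives 0.802 for n = 15 and 0.863 for n = 16. Conditional on the interval covering the mean, it gives 0.787 and 0.852, so 16 is the smallest n that reaches 80%, as stated. Allowing for losses, 16/0.90 gives 18 and 16/0.75 gives 22, also as stated.

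**2. Inputs for the selection effect.**
- SD of log Cmax: 0.65, with 0.85 as the high value (Protocol 12.8.1, 12.8.2).
- Evaluable patients: 8 at the check, 16 at the end (Protocol 12.8.2, 12.8.1).
- Reference: 101 ng/mL, the B2303 geometric mean at 5 to <15 kg (SAP 5.6).
- Model predictions at 5 mg (Protocol Table 4-2): neonates 234, ratio 234/101 = 2.32; infants 78.5, ratio 78.5/101 = 0.78.
- Assumption: the check passes if the geometric mean is within 2-fold of the reference (|mean log ratio| ≤ log 2 = 0.693).

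**3. Bias by hand, single check.** The SD of the check mean is 0.65/√8 = 0.230. With z = (log 2 − log r)/0.230, a passing check mean is low by 0.230 × φ(z)/Φ(z) on average. The final mean is low by 8/16 of that. (The lower 2-fold bound is negligible at these ratios.)
- r = 2.0: z = 0, 0.230 × 0.798 = 0.183, half is 0.092, so estimate/truth = 0.91.
- r = 2.32: z = −0.646, 0.230 × 1.249 = 0.287, half is 0.144, so 0.87.
- r = 2.5: z = −0.971, 0.230 × 1.50 = 0.345, half is 0.173, so 0.84.

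**4. Coverage by simulation** (SD 0.65, 16 final, SAP 5.7.1 interval, runs that pass; nominal upper-limit miss 5%). Where two figures are given, the first is for the single check and the second for a check at 3 and again at 8 evaluable.

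| True ratio | Dose kept | Upper limit below truth | Geometric mean / truth |
|---|---|---|---|
| 2.0 | 50%; 35% | 10%; 12% | 0.91; 0.90 |
| 2.32 | 26%; 17% | 17%; 19% | 0.87; 0.86 |
| 2.5 | 17%; 11% | 21%; 24% | 0.84; 0.83 |

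Nearly all misses are on this side. At exactly 2-fold with the single check, total non-coverage is still 10%, but almost all of it has moved to the upper limit. With SD 0.85 at 2.32 the miss is about 15% to 17% and the mean 16% to 17% low. With 20 final evaluable it is about 15% and 11%.

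**5. Where the effect is absent.** At 0.78 (single check) the upper-limit miss is about 4% and the bias under 1%. At 1.0 both are nominal. At 196-based ratio 234/196 = 1.19 the upper-limit miss is about 5%.

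**6. Other readings of the check.**
- Whole 90% CI inside the 2-fold band: miss 31% to 37% at 2.0-fold, where only 5% of doses pass.
- 90% CI contains the reference: 17% to 19% at 2.0-fold.
- 90% CI merely overlaps the band: total non-coverage 8% to 9% at 2.0- to 2.5-fold, upper-limit miss 5.2% to 6.5%, so essentially no effect there.

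**7. Patients enrolled after the check only.** Non-coverage is about 10% for these ratios under the geometric-mean check.

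**The case against.** The strongest reply has four parts.

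*The rule simulated is not in the documents.* The margin is approximate, its statistic is undefined, and the DMC also weighs other PK items, safety and efficacy. This stands: the size of the effect depends on the reading, and a lenient reading removes it.

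*The affected case is narrow.* The 9-plus-13 text describes Cohort 1, whose predicted ratio is 0.78, and there is no unsafe error there. The 2.32 divides a model value of unstated summary type by a geometric mean. Against the 196 ng/mL of Protocol Table 4-1 it becomes 1.19 and the effect vanishes. The starting dose for Cohort 2 is not fixed in advance either. All of this stands, so 2.32 is an illustration and not a forecast.

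*A reader might infer that the final 90% CI fails generally.* The documents do not support that. The inflation applies only to over-exposing doses that survive. With a starting ratio of 2.32, dose-proportional exposure, one-level steps and up to two repeats, non-coverage averaged over whichever dose is selected is 10.9% to 11.4%, with the upper limit too low in 7.6% to 7.9%.

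*A reader might infer that an over-exposing dose could be declared successful.* Protocol 12.4.2 requires the CI to contain the historical value. At 2.32 and SD 0.65 a retained dose meets this in 0.2% to 0.3% of runs. The median reported estimate is still about 2.0 times the reference. At SD 0.85 the figure is about 5%. The least favourable case (2.0-fold, SD 0.85, 16 evaluable) reaches 13% to 15%, so the criterion is rarely, though not never, met falsely.

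What remains is that the check patients are re-used unadjusted and that no planned analysis would reveal the effect if it occurred.

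**Conclusion.** The point holds in a limited form. The re-use is a plain feature of both documents. Its consequence is conditional on a dose with true exposure of about twice the reference or more surviving a check that behaves like a geometric-mean rule. In that case the upper limit is too low about two to five times as often as the nominal 5%, for true ratios of 2.0 to 2.5, and the geometric mean is understated by about 9% to 17%. These figures assume log-normal data, SD 0.65, 8 evaluable at the check and 16 at the end. Stopping enrolment at 16 evaluable (Protocol 12.8.2) with all 9 check patients evaluable raises the miss at 2.5-fold to 24% even with the single check. What is at risk is the reported size of exposure at a retained dose. The formal criterion and the Cohort 1 prediction are not seriously affected. A cheap sensitivity analysis is justified; a change to the primary analysis is not.

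**What to change.** Add to SAP 2.5.4, in words such as: *For each cohort, the geometric mean and two-sided 90% CI of ART Cmax at the retained dose level will also be calculated, by the method of Section 5.7.1, from PK-set patients enrolled after the PK check that led to expansion. The result will be shown next to the full-cohort result whichever way the two differ. For Cohort 2, the age distribution of check patients and expansion patients will be shown alongside.*

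The full-cohort interval stays primary. The age display is needed because the Cohort 2 check set starts with three patients aged 15 to 28 days, while the expansion may cover all ages or that subgroup only. A difference could therefore reflect age and not selection. Reporting should be symmetric. A rule that used the expansion-only result only when higher would be triggered in about half of trials at a true ratio of 1, and would bias the estimate upward.

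The cost is one more run of the same program and a few SAP sentences, with no new patients. The price is precision. About 8 (16 − 8) to 12 (13 × 0.9) evaluable patients remain, and the approximate expected half-width t × 0.65/√n is 1.895 × 0.65/√8 = 0.44 to 1.796 × 0.65/√12 = 0.34, against 1.753 × 0.65/√16 = 0.28 for 16. If enrolment stops early, as Protocol 12.8.2 allows, the analysis may carry little information, and the report should say so.
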